11.1 Adverse Events

11.1.1 Reportable AEs

All AEs that occur after the informed consent is signed and baseline assessments are completed (including run-in) must be recorded on the AE CRF (paper and/or electronic) whether or not related to study agent.

11.1.2 AE Data Elements:

The following data elements are required for AE reporting.

- AE verbatim term
- NCI Common Terminology Criteria for Adverse Events (CTCAE v4) AE term (MedDRA lowest level term)
- CTCAE (MedDRA) System Organ Class (SOC)
- Event onset date and event ended date
- Treatment assignment code (TAC) at time of AE onset
- Severity grade
- Attribution to study agent (relatedness)
- Whether or not the event was reported as a SAE
- Whether or not the subject dropped due to the event
- Outcome of the event

11.1.3 Severity of AEs

11.1.3.1 Identify the AE using the active CTCAE (v4). The CTCAE provides descriptive terminology (MedDRA lowest level term) and a grading scale for each AE listed. A copy of the CTCAE can be found at

http://ctep.cancer.gov/protocolDevelopment/electronic applications/ctc.htm

AEs will be assessed according to the grade associated with the CTCAE term. AEs that do not have a corresponding CTCAE term will be assessed according to the general guidelines for grading used in the CTCAE v4 as stated below.

CTCAE v4 general severity guidelines:

Grade	Severity	Description
1	Mild	Mild; asymptomatic or mild symptoms; clinical or diagnostic observations only; intervention not indicated.
2	Moderate	Moderate; minimal, local or noninvasive intervention indicated; limiting age-appropriate instrumental activities of daily living (ADL)*.
3	Severe	Severe or medically significant but not immediately life- threatening; hospitalization or prolongation of hospitalization indicated; disabling; limiting self-care ADL**.
4	Life-threatening	Life-threatening consequences; urgent intervention indicated.
5	Fatal	Death related to AE.

ADL

11.1.4 Assessment of relationship of AE to treatment

The possibility that the AE is related to study agent will be classified as one of the following: not related, unlikely, possible, probable, or definite.

11.1.5 Follow-up of AEs

All AEs, including lab abnormalities that in the opinion of the investigator are clinically significant, will be followed according to good medical practices and documented as such.

11.2 Serious Adverse Events

11.2.1 DEFINITION: Regulations at 21 CFR §312.32 (revised April 1, 2014) define an SAE as any untoward medical occurrence that at any dose has one or more of the following outcomes:

- Death
- A life-threatening AE
- Inpatient hospitalization or prolongation of existing hospitalization
- A persistent or significant incapacity or substantial disruption of the ability to perform normal life functions
- A congenital anomaly or birth defect
- Important medical events that may not be immediately life-threatening or result in death or hospitalization should also be considered serious when, based upon

^{*}Instrumental ADL refers to preparing meals, shopping for groceries or clothes, using the telephone, managing money, etc.

^{**}Self-care ADL refers to bathing, dressing and undressing, feeding self, using the toilet, taking medications, and not bedridden.

MAY2015-05-01 Version 4.0, Amendment 6 May 13, 2019

appropriate medical judgment, they may jeopardize the patient and may require intervention to prevent one of the other outcomes.

11.2.2 Reporting SAEs to DCP

11.2.2.1 The Lead Organization and all Participating Organizations will report SAEs on the DCP SAE Report Form found on the CPN website and on the DCP website at this location: http://prevention.cancer.gov/clinical-trials/clinical-trials-management/protocol-information-office/pio-instructions-and-tools/2012-consortia.

11.2.2.2 Contact the DCP Medical Monitor by email (preferred) or phone within 24 hours of knowledge of the event.

[name] [name], FACS
National Institutes of Health, National Cancer Institute, Division of Cancer Prevention
[name]
[name]

[contact]

Fax (with cover sheet, Attn: [name]): [contact]

Email: [contact]

Include the following information when contacting the Medical Monitor:

- Date and time of the SAE
- Date and time of the SAE report
- Name of reporter
- Call back phone number
- Affiliation/Institution conducting the study
- DCP protocol number
- Title of protocol
- Description of the SAE, including attribution to drug

11.2.2.3 The Lead Organization and all Participating Organizations will submit SAE reports within 48 hours of learning of the event via the current, approved SAE reporting process:

The following individuals/entities will be provided with the SAE information within the 48 hour time frame:

- 1. The DCP Medical Monitor at [contact]
- 2. DCP's Regulatory Contractor CCS Associates, Inc. (CCSA; [contact]) at [contact]
- 3. The CPN Operations Office at [contact]
- 11.2.2.4 The DCP Medical Monitor and CCSA regulatory and safety staff will determine which SAEs require FDA submission as IND safety reports.

11.2.2.5 The Lead Organization and all Participating Organizations will comply with applicable regulatory requirements related to reporting SAEs to the CIRB/IEC.

11.2.3 Follow-up of SAE

Participating organization (PO) staff will submit follow-up reports as soon as they are available via the current, approved SAE reporting process. SAEs will be followed and treated according to institutional standards of good clinical practice. SAEs that are at least possibly related to study intervention will be followed until resolution.

12. STUDY MONITORING

12.1 Data Management

The Mayo Clinic Cancer Center database will be the database of record for the protocol and subject to NCI and FDA audit. Minimum Data Sets will be submitted to DCP per contract requirements. Please see 2012 CPN Master Data Management Plan.

12.2 Case Report Forms

Participant data will be collected using protocol-specific case report forms (CRF) utilizing NCI-approved Common Data Elements (CDEs). The approved CRFs will be used to create the electronic CRF (e-CRF) screens for data entry into the Mayo Clinic Cancer Center database. Amended CRFs will be submitted to the DCP Protocol Information Office for review and approval.

12.3 Source Documents

A source document is any document, form, or record where *specific participants'* data are first recorded. FDA [21 CFR 312.62 (b)] requires that the investigator "...prepare and maintain accurate case histories designed to record all observations and other data pertinent to the investigation on each individual treated with the investigational agent or employed as a control in the investigation." Among many other items, source documents include:

- Inpatient and outpatient medical records
- Progress notes
- Consults
- Nursing notes
- Pathology reports
- Endoscopy reports
- Medicine/radiation administration records
- Surgical reports
- Laboratory reports

- Admission forms
- Flow sheets and worksheets that are signed and dated
- Protocol or study road maps
- Appointment books
- Participant diaries/calendars
- Blood and tissue collection/submission requisition forms (signed and dated).
- Case Report Forms (signed and dated):
 - Symptoms: Pre-Intervention
 - Physical Exam

Specimen Submission: BloodSpecimen Submission: Tissue

12.4 Data and Safety Monitoring Plan

The CPN Master DSMP, applicable to all studies within the CPN Consortium, has been modified for the purposes of this study. The MAY2015-05-01 DSMP provides detailed information regarding data and safety monitoring for this study. The trial will be monitored closely for occurrence of adverse events by the study team and by the Mayo Clinic Cancer Center Data Safety Monitoring Board (DSMB). The DSMB (along with the study Medical Monitor) will be consulted regarding whether or not accrual should be suspended to allow for investigation in the occurrence of severe adverse events, particularly for those that are possibly, probably, or definitely related to the study agent.

12.5 Sponsor or FDA Monitoring

The NCI, DCP (or their designee), pharmaceutical collaborator (or their designee), or FDA may monitor/audit various aspects of the study. These monitors will be given access to facilities, databases, supplies and records to review and verify data pertinent to the study.

12.6 Record Retention

Clinical records for all participants, including CRFs, all source documentation (containing evidence to study eligibility, history and physical findings, laboratory data, results of consultations, etc.), as well as IRB records and other regulatory documentation will be retained by the Investigator in a secure storage facility in compliance with Health Insurance Portability and Accountability Act (HIPAA), Office of Human Research Protections (OHRP), Food and Drug Administration (FDA) regulations and guidances, and NCI/DCP requirements, unless the standard at the site is more stringent. The records for all studies performed under an IND will be maintained, at a minimum, for two years after the approval of a New Drug Application (NDA). For NCI/DCP, records will be retained for at least three years after the completion of the research. NCI will be notified prior to the planned destruction of any materials. The records should be accessible for inspection and copying by authorized persons of the Food and Drug

Administration. If the study is done outside of the United States, applicable regulatory requirements for the specific country participating in the study also apply.

12.7 Cooperative Research and Development Agreement (CRADA)/Clinical Trials Agreement (CTA)

The agent supplied by DCP, NCI, used in this protocol, is provided to the NCI under a Collaborative Agreement (CRADA, CTA) between Thorne Research, Inc. (hereinafter referred to as Collaborator) and the NCI Division of Cancer Prevention. Therefore, the following obligations/guidelines, in addition to the provisions in the "Intellectual Property Option to Collaborator" contained within the terms of award, apply to the use of Agent in this study:

- 12.7.1 Agent may not be used for any purpose outside the scope of this protocol, nor can Agent be transferred or licensed to any party not participating in the clinical study. Collaborator data for Agent are confidential and proprietary to Collaborator and shall be maintained as such by the investigators. The protocol documents for studies utilizing investigational agents contain confidential information and should not be shared or distributed without the permission of the NCI. If a patient participating on the study or participant's family member requests a copy of this protocol, the individual should sign a confidentiality agreement. A suitable model agreement can be downloaded from the DCP website.
- 12.7.2 For a clinical protocol where there is an Investigational Agent used in combination with (an) other investigational Agent(s), each the subject of different collaborative agreements, the access to and use of data by each Collaborator shall be as follows (data pertaining to such combination use shall hereinafter be referred to as "Multi-party Data").
- 12.7.3 NCI must provide all Collaborators with prior written notice regarding the existence and nature of any agreements governing their collaboration with NIH, the design of the proposed combination protocol, and the existence of any obligations that would tend to restrict NCI's participation in the proposed combination protocol.
- 12.7.4 Each Collaborator shall agree to permit use of the Multi-Party Data from the clinical trial by any other Collaborator solely to the extent necessary to allow said other Collaborator to develop, obtain regulatory approval, or commercialize its own investigational agent.
- 12.7.5 Any Collaborator having the right to use the Multi-Party Data from these trials must agree in writing prior to the commencement of the trials that it will use the Multi-Party Data solely for development, regulatory approval, and commercialization of its own investigational agent.
- 12.7.6 Clinical Trial Data and Results and Raw Data developed under a collaborative agreement will be made available exclusively to Collaborator, the NCI, and the FDA, as appropriate. All data made available will comply with HIPAA regulations.

12.7.7 When a Collaborator wishes to initiate a data request, the request should first be sent to the NCI, who will then notify the appropriate investigators of Collaborator's wish to contact them.

12.7.8 Any manuscripts reporting the results of this clinical trial must be provided to DCP for immediate delivery to Collaborator for advisory review and comment prior to submission for publication. Collaborator will have 30 days (or as specified in the CTA) from the date of receipt for review. Collaborator shall have the right to request that publication be delayed for up to an additional 30 days in order to ensure that Collaborator's confidential and proprietary data, in addition to Collaborator's intellectual property rights, are protected. Copies of abstracts must be provided to DCP for forwarding to Collaborator for courtesy review as soon as possible and preferably at least three days prior to submission, but in any case, prior to presentation at the meeting or publication in the proceedings. Press releases and other media presentations must also be forwarded to DCP prior to release. Copies of any manuscript, abstract, and/or press release/ media presentation should be sent to the Protocol Information Office at NCI DCP [contact].

The Protocol Information Office will forward manuscripts to the DCP Project Officer for distribution to the Collaborator. No publication, manuscript or other form of public disclosure shall contain any of Collaborator's confidential/proprietary information.

13. STATISTICAL CONSIDERATIONS

13.1 Study Design/Description

The primary endpoint of this randomized trial is to compare the absolute change in IL-1 β cytokine levels in the gastric mucosa from baseline to 6 months among participants randomly assigned to receive either Meriva® or placebo. We will also assess many secondary and translational endpoints.

There are limited Quality of Life (QOL) data on participants who participate in chemoprevention trials, and we intend to create a databank of QOL information by administering the "Was It Worth It" (WIWI) questionnaire at trial completion across multiple trials. We will seek to evaluate participant perception of their experience in trial participation once we have a reasonable amount of information (large enough sample size). Since participants who participate in these chemoprevention trials are high risk but otherwise healthy, the WIWI tool would help answer simple questions about participants' assessment of whether or not participation in this trial was "worth it." This is an optional questionnaire, which participants may decline to complete.

13.2 Randomization/Stratification

Participants will be randomized in a 1:1 fashion to one of two arms (Meriva® vs. placebo), using a dynamic allocation procedure called the Pocock-Simon, which balances the marginal distributions of the stratifications factors across the intervention groups and has been shown to be able to accommodate a large number of factors (10-20) without difficulty. For this study we will use the following stratification factors (collected at baseline, prior to randomization): enrolling site (Honduras or Puerto Rico) and gastric mucosal histologic diagnosis (MAG, GIM, or both).

13.3 Accrual and Feasibility

Planned Accrual Estimates

	DOMESTIC PLANNED ENROLLMENT REPORT Ethnic Categories					
Racial Categories	Not Hispanic or Latino		Hispanic or Latino			
	Female	Male	Female	Male	Total	
American Indian/Alaska Native	0	0	0	0	0	
Asian	0	0	0	0	0	
Native Hawaiian or Other Pacific Islander	0	0	0	0	0	
Black or African American	0	1	0	0	1	
White	1	0	5	16	22	
More Than One Race	0	0	1	1	2	
Total	1	1	6	17	25	

	INTERNATIONAL PLANNED ENROLLMENT REPORT Ethnic Categories					
1000 2000 000 100 ISS.						
Racial Categories	Not Hispanic or Latino		Hispanic or Latino		¥1. II	
	Female	Male	Female	Male	Total	
American Indian/Alaska Native	0	0	0	0	0	
Asian	0	0	0	0	0	
Native Hawaiian or Other Pacific Islander	0	0	0	0	0	
Black or African American	0	0	0	1	1	
White	1	0	5	16	22	
More Than One Race	0	0	1	1	2	
Total	1	0	6	18	25	

The study design requires a total of 100 participants for screening evaluation with approximately 50 moving forward to randomization (25 total participants per arm) due to anticipated screen failures of up to 50% prior to randomization. We further expect up to 12% of participants to drop out or otherwise become non-evaluable by 6 months, leaving 22 evaluable subjects per arm for the primary endpoint evaluation. We expect to randomize an average of 2-4 participants per month for each of the two participating CPN sites (Puerto Rico and Honduras), for an overall average accrual rate of 5-6 participants per month.

Amendment 6 Update: Because of delays related to regulatory and customs approvals, activation at Honduras was delayed by 15 months, which resulted in slower than expected overall accrual. Recently, the Honduras site discovered a higher than expected incidence of *Helicobacter pylori* infection, an exclusion criterion. In order to continue their expected recruitment pace, they expanded their outreach to more rural areas where *H. pylori* infection is somewhat less prevalent. They have also begun contacting participants who were screen failures in one previous study and who have completed another previous study as a group of known potential participants with high rates of study compliance. They are also reviewing lists of *H. pylori*-treated participants for evidence of gastric metaplasia and possible eligibility. The current anticipated completion date (last participant contact for the primary endpoint) is the 4th quarter of 2020.

13.4 Primary Objective, Endpoint(s), Analysis Plan

The primary endpoint of this randomized trial is to compare the absolute change in IL-1 β cytokine levels (measured by Luminex assay) in the gastric mucosa from baseline to 6 months among participants randomly assigned to receive either Meriva® or placebo. Statistical considerations regarding sample size and study power are based on this primary study endpoint.

In total, approximately 100 individuals will be screened and 50 participants will be randomized to receive Meriva® (n=25) or placebo (n=25), in order to achieve complete trial data on 22 evaluable participants in each arm (44 evaluable total). This assumes a 10% over accrual buffer after randomization to account for participants who are deemed ineligible, cancel, or dropout for other reasons during the intervention period. We expect to randomize approximately 5-6 participants per month across both the Puerto Rico and Honduras recruiting sites.

The null hypothesis for this study is that the absolute change in the IL-1 β values from baseline to 6 months is the same or increased for Meriva® vs. placebo. The alternative hypothesis is that Meriva® intervention will lead to a significant decrease in IL-1 β cytokine levels from baseline to 6 months, as compared to placebo. The proposed sample size and power calculations are based on prior unpublished data, where IL-1 β levels are expected to have a mean of approximately 14 pg/mg protein at baseline, with a standard deviation of about 7.5 pg/mg of protein. This prior mouse study showed a 2-fold decrease in IL-1 β levels for curcumin-treated mice (from around 14 to 7 pg/mg protein, comparing the vehicle [equivalent to placebo] treated to curcumin-treated mice). Based on this prior data, we expect the Meriva®-treated participants to have a mean decrease of about 7 pg/mg of protein or more by 6 months after baseline, leading to a 6 month IL-1 β mean of 7 pg/mg of protein in the Meriva®-treated participants (2-fold decrease). For the placebo group, we expect the mean IL-1 β to either stay the same or decrease slightly from baseline to 6 months.

With 22 evaluable participants per arm, this study yields 88% power to detect a mean decrease of 7 pg/mg protein or more in IL-1 β level in the Meriva® intervention arm compared to a mean decrease of 0.5 pg/mg protein in the placebo arm (from baseline to 6 months), with an overall 1-sided significance level of 0.05 (2 sample t-test, assuming the same standard deviation of 7.5 pg/mg protein in each arm). If the data are not normally distributed, we will use the Wilcoxon Rank-Sum test for the primary endpoint analysis.

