Population Health Perspective: The Central America Four (CA4) nations (Honduras, El Salvador, Guatemala, and Nicaragua) form the core low/middle income (LMIC) region in the western hemisphere. The CA4 is unified by its geography, history, language, and culture. These countries opened their borders in 2006, and are in transition towards a union of their health systems and infrastructures. A regional approach to cancer control is essential, and cancer capacity-building is imperative. The CA4 population is nearly 35 million, with an estimated immigrant population of 4-5 million, making it unique for cancer control among global LMICs from a U.S. perspective, given the burgeoning U.S. Hispanic population. The Honduras-Puerto Rico partnership in gastric cancer truly provides a unique and powerful platform for chemoprevention and clinical translational studies in Hispanic populations, and the two proposed study sites have characteristics that are appeasing for the current study design, which include:

- Puerto Rico and Central America (Honduras) have a high prevalence of GIM (detected in approximately 20% of asymptomatic patients in the Endoscopy Clinics). However, the sites have different gastric cancer incidence rates,² which will be noted by the use of stratification factors.
- In both Puerto Rico and Honduras, curcumin is not part of the local diet, nor is it readily available. Therefore, dietary curcumin will not be a confounder in the proposed study setting.

[figure not shown]

Figure 1. Meriva reduces gastritis and modulates cytokine responses in murine H. pylori infection.

Findings:

A. Curcumin levels were measured by mass spectrometry in different sites; S, serum; ST, Stomach; SI, small intestine; and C, colon.

B: Quantification of *H. pylori* colonization and histologic gastritis. Veh, vehicle (equivalent to placebo); Mer, Meriva.

C: Representative H&E staining of mouse stomach tissues, showing reduced mucosal thickening and inflammatory cell infiltration with Meriva.

D and **E**: Cytokine levels measured in stomach tissue lysates by the Luminex assay (multiplex bead array). Note in panels D and E, "uninfected" implies never-infected in the mouse model; in human populations, nearly all subjects with IM have had chronic *H. pylori* infection, but may not have measurable active infection in midadulthood. Note that IL-10 is a recognized anti-inflammatory cytokine, demonstrating a potential protective effect from Meriva in panel E.

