3. SUMMARY OF STUDY PLAN

General Overview: Chronic multifocal atrophic gastritis (MAG) and gastric intestinal metaplasia (GIM) are established precancerous lesions. Participants with MAG, GIM, or both will be identified or confirmed at the baseline upper endoscopy. Willing, eligible trial participants will then be registered and randomized to receive either Meriva® 1000 mg (one 500mg capsule twice per day for a total curcuminoid intake of 200 mg/day) or matching placebo (1 capsule twice per day). A follow-up upper endoscopy will be performed at 6 months (See Schema). We anticipate that the majority of enrolled subjects will have GIM, which confers higher gastric cancer risk. Therefore, baseline histology will be used for stratification.

Screening and Baseline: At both the Puerto Rico and Honduras recruitment sites, potential study participants with a confirmed or suspected diagnosis of gastric MAG and/or GIM will be pre-selected using detailed clinical and research databases that are currently in place and have been demonstrated to be effective for recruitment purposes in other recent studies. Participants who meet the inclusion and exclusion criteria will undergo a comprehensive history and physical examination, alcohol and tobacco use assessments, eligibility/baseline blood testing, *H. pylori* stool antigen testing, research blood collection, and upper endoscopy with biopsies.

Randomization: Eligible participants will be randomized in a 1:1 fashion to 1000 mg Meriva® (one 500mg capsule twice per day, for a total of 200 mg curcuminoids/day) or matching placebo for a 6-month intervention period, using a dynamic allocation procedure called the Pocock-Simon³⁵ that balances marginal distributions of the stratification factors across defined intervention groups and has been shown to be able to accommodate a large number of factors (10-20) without difficulty.³⁶ The randomization will be stratified based on enrolling site (Honduras or Puerto Rico) and baseline gastric mucosal histologic diagnosis (MAG, GIM, or both). The study teams will make weekly phone calls to the participants, and participants will return at 3 months for the assessment of adverse events, blood tests for safety and toxicity, protocol compliance, and concomitant medication usage.

End of Intervention: Participants will return at 6 months for a physical exam; research blood collection, assessment of adverse events, protocol compliance, and concomitant medication

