6.8.2 Registration

- 6.8.2.1 To register a participant, the participating site will send the completed Registration Eligibility Checklist to the CPN Registration Office (Email: [contact]; [contact]). The CPN Registration Office will enter the information into the CPN-hosted database. For randomization details, see Section 13.2.
- 6.8.2.2 Intervention cannot begin prior to registration and must begin ≤ 14 days from registration.
- 6.8.2.3 Pathology reports confirming diagnoses will be placed in the study participant's file \leq 30 days post Registration/Randomization.
- 6.8.2.4 Once the intervention assignment has been ascertained by the CPN Registration Office, the participant's study medication code numbers will be displayed on the emailed confirmation page. At least two weeks prior to the Month 3 visit, the data manager/nurse/pharmacist at the participant's institution must contact the CPN Registration Office at [contact] for code numbers when additional study product is needed for the participant.
- 6.8.2.5 Stratification Factors collected at baseline (prior to randomization):
 - Enrolling Site: Honduras versus Puerto Rico
 - Gastric mucosal histologic diagnosis: MAG versus GIM versus Both (from screening EGD)

After the participant has been registered on to the study, values of the stratification factors will be recorded. Randomization will be performed by CPN personnel. The CPN electronic-based randomization system will be utilized to ensure that randomization of participants to appropriate study arms while balancing the stratification variables is carried out successfully.

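### Allocation is minimized on site and histology, but the primary test uses neither; adjusting for both is a low-cost gain if they predict change in IL-1β

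*Combined protocol and SAP*

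**What the plan says.** Sections 3 and 13.2 randomize 1:1 with a dynamic procedure that "balances the marginal distributions of the stratifications factors across the intervention groups". The factors are enrolling site (Honduras or Puerto Rico) and histology, listed in Section 6.8.2 as "Gastric mucosal histologic diagnosis: MAG versus GIM versus Both (from screening EGD"). Both are recorded before randomization.

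The reasons given for the factors concern cancer, not cytokines. Section 2.3 cites the sites' different gastric cancer incidence, "which will be noted by the use of stratification factors". Section 3 says "We anticipate that the majority of enrolled subjects will have GIM", which carries the higher cancer risk.

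Section 13.4 compares change in IL-1β between arms "with an overall 1-sided significance level of 0.05 (2 sample t-test"). If the data are not normal, "we will use the Wilcoxon Rank-Sum test for the primary endpoint analysis". Sections 13.5, 13.6 and 13.8 add no adjusted, stratified or re-randomization analysis of the primary endpoint. Section 13.8 promises 95% confidence intervals for it.

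**The concern.** The plan builds balance into the allocation and then ignores it in the test. Suppose a balanced factor predicts the change in IL-1β. The arms then have nearly the same mix of that factor, so it contributes almost nothing to the error in the arm difference. The two-sample t-test does not know this: its pooled SD still contains the between-site and between-histology spread. The standard error is too large, the true one-sided level falls below 0.05, and the interval is wider than the design warrants.

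The condition is narrow. The endpoint is a change score, so a factor that shifts both visits equally disappears on subtraction.

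This is the trial's only powered comparison, with 44 evaluable participants. Section 13.3 adds that "activation at Honduras was delayed by 15 months" and that its recruitment sources have since widened. The site populations may therefore differ, although this does not show that change in IL-1β differs.

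**Working it through.** **Inputs from Sections 13.2 to 13.4.** 50 randomized, 22 evaluable per arm, mean decrease 7 versus 0.5 pg/mg (difference 6.5), SD 7.5, one-sided 0.05, two sites planned at 25 each, three histology levels.

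**Stated power.** The standard error is 7.5 × √(2/22) = 2.26 and the noncentrality is 6.5/2.26 = 2.87. With 42 degrees of freedom, one-sided 0.05, power is 88.2%, against 88% stated. This requires 7.5 to be the SD of change. Section 13.4 introduces it as the spread of levels "at baseline, with a standard deviation of about 7.5 pg/mg of protein". With an SD of 7.5 at each visit and within-person correlation r, the SD of change is 7.5 × √(2(1 − r)):

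- r = 0.7: SD 5.8, power 97.8%
- r = 0.5: SD 7.5, power 88.2%
- r = 0.3: SD 8.9, power 77.2%

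**Mechanism.** Let R² be the share of the variance of change predicted by site and histology. Under perfect balance the true standard error is about √(1 − R²) times the one the t-test uses: 0.95, 0.89 and 0.84 at R² = 10, 20 and 30%.

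**Simulation, 20,000 trials per setting.** 50 participants were minimized and 44 kept at random. Assumptions not in the documents: biased coin 0.8; histology mix MAG/GIM/both 15/50/35% with equally spaced effects; variance split equally between site and histology; all R² values. The SD of change is 7.5.

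| R² | t-test level | Power, t-test | Power, adjusted | Gain (points) | 95% width, t-test | 95% width, adjusted |
|---|---|---|---|---|---|---|
| 0% | 5.1% | 88.1% | 87.5% | -0.6 | 9.08 | 9.20 |
| 5% | 4.8% | 88.5% | 88.8% | +0.3 | 9.10 | 8.97 |
| 10% | 4.3% | 88.6% | 89.9% | +1.4 | 9.12 | 8.74 |
| 20% | 4.0% | 89.8% | 93.0% | +3.2 | 9.11 | 8.24 |
| 30% | 3.2% | 90.7% | 95.3% | +4.6 | 9.11 | 7.69 |

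Gains are taken before rounding. The adjusted model's level is 4.9-5.2%. The interval narrows by 1 − 8.74/9.12 = 4% at R² = 10% and by 1 − 7.69/9.11 = 16% at 30%.

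A separate run with a 10/60/30% histology mix gave t-test levels of about 4.4% and 3.0% at R² = 10% and 30%. Under simple 1:1 randomization the same t-test stayed at 5.0% at both shares, so the conservatism comes from the minimization.

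**Factors that predict only the stable level** (10/20/30% of its variance, r = 0.5). The t-test level is 5.0/5.3/5.1%; power is 88.3/88.4/88.2% unadjusted and 87.8/87.5/87.5% adjusted. There is no gain.

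**With baseline IL-1β already in the model** (r = 0.5). Adding the factors changes power by -0.5/+0.5/+1.2/+2.5/+3.6 points at R² = 0/5/10/20/30%.

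**Other SDs of change**, at R² = 0/10/20/30%. With 5.8 the gain is -0.2/+0.4/+0.6/+0.9 points; with 8.9 it is -1.2/+1.9/+4.8/+8.2.

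**Fallback**, rank-sum versus covariance analysis of ranks, at R² = 0/10/20/30%:

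- Normal: 86.0/86.7/87.7/89.1% versus 85.2/88.1/91.3/94.0%
- t with 4 df: 94.4/94.0/93.4/93.3% versus 94.0/95.0/96.2/97.2%
- Log-normal: 99.0/98.8/98.1/97.6% versus 98.9/99.1/99.0/99.2%

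The level of the rank covariance test is 4.7-5.2%. A rank test stratified on all six site-by-histology cells also holds its level, but at R² = 0 it loses 5.7 points on normal data. The linear model's 95% interval covers 95.1-95.8% under the two non-normal shapes.

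**Robustness at R² = 20%.** With coins of 0.7/0.9/1.0 the gain is 3.5/3.0/3.1 points; with a 70/30 site split it is 3.3. Across all settings, the choice of how to merge a histology level with under 5 participants moves power by at most 0.9 points.

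**The case against.** The planned test is valid, prespecified and correctly powered on its own inputs, so no error is shown.

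Shares of 10-30% also imply large effects. With 50/50 sites and half the share each, the sites' difference in mean change is 15 × √(R²/2) = 3.4, 4.7 and 5.8 pg/mg at R² = 10, 20 and 30%. The range across histology levels is about 4.9 pg/mg at 10% and 8.6 at 30%. The hypothesized drug effect is 6.5, and Section 13.4 expects little or no mean change on placebo. At 5% or less the gain is negligible, and on log-normal data the fallback gains only 0.3-1.6 points at 10-30%.

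Baseline IL-1β would buy more: at r = 0.5, power rises from about 88% to 94%. And because the analysis plan is protocol Section 13, replacing the primary test needs a protocol amendment while recruitment is under way.

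Most of this stands as a limit on size. The upper shares are demanding, although Section 13.4's expectation is an overall mean and does not exclude subgroup shifts that cancel. The amendment is a real administrative step. Neither point removes the mismatch between allocation and analysis, and the loss when the factors predict nothing is about 1 point or less. The gain from baseline IL-1β is a separate matter; site and histology can still add to it.

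**Conclusion.** The concern holds as a conditional point of efficiency and calibration, and the change should be made. If site and histology predict 10-30% of the variance of change, the planned t-test runs at about 4.3-3.2% instead of 5%, and adjustment recovers about 1.4-4.6 points of power. If they predict 5% or less, or only the level, the difference is under 1 point either way at an SD of change of 7.5. At that SD the planned test keeps about 88% power or more in every setting, so nothing in it is invalid.

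The size rests on an R² that the documents do not give, and on the assumed histology mix, coin and effect pattern. Adjustment helps most where the plan is weakest: at an SD of change of 8.9, planned power is 77.2% and the gain reaches 8.2 points at R² = 30%.

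**What to change.** In Section 13.4:

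- Make the primary analysis a linear model of change in IL-1β with arm, site and histology as main effects, using histology as recorded at randomization, tested one-sided at 0.05. Report the adjusted arm difference in pg/mg with its 95% interval.
- Prespecify, blind to arm, when and how a sparse histology level is merged. Which levels to merge is the sponsor's choice.
- If normality fails, test by covariance analysis of the ranks of change with the same factors, and still report the adjusted mean difference with its interval.
- Keep the unadjusted t-test and rank-sum test as sensitivity analyses.
- If baseline IL-1β is added, keep site and histology in the model.
- State whether 7.5 pg/mg is the SD of change.

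The cost is wording, submitted as an amendment under Section 14.3; no new data are needed. The model uses up to three degrees of freedom (site 1, histology 2). If the factors predict nothing, the linear model loses 0.5-0.8 points of power at an SD of change of 7.5 (0.2 at 5.8, 1.2 at 8.9), and the rank version 0.1-0.8.
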